9.0 STUDY TREATMENT**9.1 Study Drug Administration****9.1.1 PLX9486**

Study drug PLX9486 tablets, 50 mg strength, should be taken orally as defined for each cohort, with approximately 240 mL (8 oz.) of water. Study drug should be taken at approximately the same times of day. Study drug should be swallowed whole and not crushed, chewed, or dissolved in water. A dosing period of up to 1 hour is permissible if required by the number of tablets to be taken or as convenient for the patient.

For patients taking PLX9486 on a BID (twice daily) dosing schedule, the evening dose should be taken approximately 12 hours after the morning dose.

For patients taking PLX9486 on a QD (once daily) dosing schedule, the dose should be taken at the same times of the day and approximately 24 hours apart.

If more than 2 hours have elapsed from the scheduled time of dosing, the dose should be considered missed. Missed doses should be skipped and not taken as a double dose at the next dosing time point. Patients who vomit their dose should be instructed NOT to make up that dose.

Patients may take their PLX9486 medication, whether as a single agent or in combination with PLX3397 or sunitinib. If patients choose to take their medication with food, dosing should occur within approximately 30 minutes of a meal or snack or no later than approximately 1 hour after a meal. As of Amendment 6, patients who were previously instructed to fast for 8 hours prior to dosing are no longer required to fast and may now take their study medication with food.

9.1.2 PLX3397

The study treatment PLX3397 HCl is supplied in 200 mg immediate-release capsules for oral administration.

As of Amendment 6, PLX3397 should be administered once a day, and may be taken with food and can be taken with approximately 240 mL (8 oz.) of water. For subjects instructed to take PLX3397 as BID and on an empty stomach before Amendment 6, the dosing regimen should change to QD going forward and it may be taken with food. The dose should be taken at approximately the same times of the day and approximately 24 hours apart for QD dosing. Study drug should be swallowed whole and not crushed, chewed, or dissolved in water. A dosing period of up to 1 hour is permissible if required by the number of tablets to be taken or as convenient for the patient.

For patients receiving both PLX9486 and PLX3397, the medications may be taken together at the same time and may be taken with food. For patients who are taking PLX9486 and PLX3397 with food, the drugs should be taken within approximately 30 minutes of a meal or snack or no later than approximately 1 hour after a meal. If more than 2 hours have elapsed from the scheduled time of dosing, the dose should be considered missed. Missed doses should be skipped and not taken as a double dose at the next dosing time point. Subjects who vomit their dose should be instructed NOT to make up that dose.

9.1.3 Sunitinib

Sunitinib is commercially available. Please refer to the USPI for further prescribing information. Sunitinib tablets should be taken orally as defined for each cohort, with approximately 240 mL (8 oz.) of water. For patients receiving both PLX9486 and sunitinib, the medications may be taken together at the same time and may be taken with food. For patients who are taking PLX9486 and sunitinib with food, the drugs should be taken within approximately 30 minutes of a meal or snack or no later than approximately 1 hour after a meal. Study drug should be taken at approximately the same times of day. Study drug should be swallowed whole and not crushed, chewed, or dissolved in water. A dosing period of up to 1 hour is permissible if required by the number of tablets to be taken or as convenient for the patient. As of Amendment 6, patients who were previously instructed to fast for 8 hours prior to dosing are no longer required to fast and may now take their study medication with food.

If more than 2 hours have elapsed from the scheduled time of dosing, the dose should be considered missed. Missed doses should be skipped and not taken as a double dose at the next dosing time point. Subjects who vomit their dose should be instructed NOT to make up that dose.

9.1.4 Dosing on PK Sample Collection Days

On PK sample collection days, subjects should be instructed *not* to take their morning dose of PLX9486 and PLX3397 or sunitinib (if applicable) at home before the clinic visit. The time of dosing will be recorded in the clinic. For Part 2b and [REDACTED], the evening dose of PLX3397 will be taken by the subject at home. On non-PK sample collection days, the subject will administer PLX9486 (and PLX3397 or sunitinib if applicable) independently and record dosing information in the study drug administration diary.

For patients in all parts of the study, one PK sample should be collected at the end of study visit for all patients and if feasible up to 4 additional PK samples may be obtained on Days 3, 7, 10, and 14 after the last dose.

9.2 Dose Levels for Parts 1 and 2

9.2.1 Dose Escalation

9.2.1.1 Part 1: Dose-escalation Cohorts

The initial dosing regimen of PLX9486 will be daily by oral administration. Each treatment cycle will be 28 days.

Cohorts of patients will be enrolled using the standard “3+3” design. The starting dose level of PLX9486 will be 250 mg/day (Cohort 1) using a once-daily (QD) dosing regimen. For higher total daily doses, a split dosing schedule (e.g., twice-daily [BID]) may be used at the current dose level under study or with previously studied daily dose levels. In the absence of Grade ≥ 2 toxicity that is considered “possibly” or “probably” related to the study agent or dose-limiting toxicity (DLT) and in conjunction with review of the PK data, dose escalation is planned to occur as indicated in [Table 16](#) and as stipulated below.

Table 16: PLX9486 Administration in Part 1: Initial and Potential Dose-escalation Cohorts

Cohort Number	PLX9486 Dose Level (mg/day) ^a	Number and Unit Strength
4	1000	20 × 50 mg
5	500 (BID)	10 × 50 mg (BID)
6	1500	30 × 50 mg
7	2000	40 × 50 mg

^a Dosing interval/frequency will be QD unless otherwise specified (e.g., BID dosing).

Further dose escalation or de-escalation may be considered depending upon safety and PK findings and discussion between the Sponsor and the investigators. Dose escalation will continue unless there are dose-limiting toxicities in ≥ 2 of at least 6 patients (i.e., 33%) in one cohort within the first 28 days.

Also, dose escalation and reduction in smaller increments may be undertaken at any time based upon emerging safety, PK, and PD data.

If a DLT is observed in one patient in the initial cohort of 3 patients, an additional 3 patients will be treated at that dose (see [Section 9.3](#)). If DLT is observed in 2 or more patients of either 3 or 6 patients (i.e., $\geq 33\%$ of patients treated) at a dose level, then a lower dose level of PLX9486 may be introduced unless no further reductions are feasible. If no DLT is observed, the recommended dose for further evaluation may be established based on toxicity, PK, and convenience of dosing in approximately 3 to 6 patients treated at that dose. Dose escalation will only be permitted if adequate safety and tolerability have been demonstrated at the previous lower dose for 28 days.

In addition, if the Study Committee ([Section 10.1.1](#)) determines that, in the absence of DLTs, enrollment of additional patients is required in order to better understand PK, safety, or pharmacodynamic markers in specific patient types (e.g., patients with exon 17 mutations), an additional 3 patients may be undertaken at one or more of the dose levels already studied or currently being studied. Alternatively, a split dosing schedule (e.g., BID) may be studied at the current dose level under study or previously studied daily dose levels. Should more than 3 patients be accrued to a dose level for reasons other than DLT/toxicity, the decision to escalate further may be made after the first 3 patients clear the DLT window period after review of the available data by the Study Committee.

Once the safety and tolerability of a dose level have been established by all patients enrolled into the dose level cohort and treated for at least 28 days, intra-patient dose escalation to that dose level will be permitted for patients at lower dose levels who have not experienced a Grade 3 or higher treatment-related toxicity that has not resolved. Additional PK samples may be requested for patients who dose escalate. In addition, additional PK samples may be requested for patients who experience a SAE, DLT, or adverse event of special interest (AESI).

9.2.1.2 Part 2: Extension Cohorts

[REDACTED]

Part 2b. Cohorts of patients will be enrolled using the standard “3+3” design. The PLX9486 dose escalation may follow the pattern established in Part 1, starting at $\leq 50\%$ of the MTD/RP2D established in Part 1. In the absence of Grade ≥ 2 toxicity that is considered “possibly” or “probably” related to the study agent and in conjunction with review of the pharmacokinetic data, dose escalation in Part 2b is planned to occur as indicated in [Table 17](#).

Table 17: PLX9486 and PLX3397 Administration in Part 2b: Initial and Potential Dose-escalation Cohorts

Cohort Number	PLX9486 Dose Level (mg/day) ^a	PLX3397 Dose Level (mg/day)
1	Approximately 50% of Part 1 RP2D	600 (200 mg in AM and 400 mg in PM)
2	Approximately 100% of Part 1 RP2D	600 (200 mg in AM and 400 mg in PM)
3	100% of Part 1 RP2D	400 mg QD (Cycles 1 and 2)
		600 mg QD (Cycle 3 +) ^b
4 +	TBD ^c	TBD ^c

RP2D = recommended phase 2 dose; TBD = to be determined

^a PLX9486 administered once-daily (QD) or for higher total daily doses, as split doses (e.g., twice-daily [BID]).

^b At the discretion of the investigator and in the absence of clinically significant drug-related toxicity ([Section 9.3](#)) during Cycles 1 and 2.

^c Based on a review of the data by the Study Committee.

Dose escalation will continue unless there are DLTs in ≥ 2 of 6 patients in one cohort within the first 28 days of continuous dosing.

[figure not shown]
Further dose escalation and reduction in smaller increments may be undertaken at any time based upon emerging safety, PK, and PD data. Dose adjustments may also include increasing the number of patients at a given dose level as a result of the review of safety and PK data by the Sponsor and investigators. In addition, alternative dosing schedules may be explored, such as continuous dosing followed by a rest period, staggered dosing of the agents, etc., depending on the safety, PK, or PD-generated data, as well as data from other ongoing PLX3397 studies.

If a DLT is observed in one patient at a given cohort, an additional 3 patients will be enrolled into the cohort. If DLT is observed in ≥ 2 of at least 6 patients (i.e., $\geq 33\%$) at a dose level, then a lower dose level of PLX9486 may be introduced to the combination regimen. If no DLT is

observed, the recommended dose for further evaluation may be established based on toxicity, PK, and convenience of dosing in approximately 3 to 6 patients treated at that dose. Dose escalation will only be permitted if adequate safety and tolerability have been demonstrated at the previous lower dose for 28 days.

In addition, if the Study Committee ([Section 10.1.1](#)) determines that, in the absence of DLTs, enrollment of additional patients is required in order to better understand PK, safety, or pharmacodynamic markers in specific patient types (e.g., patients with exon 17 mutations), an additional 3 patients may be undertaken at one or more of the dose levels already studied or currently being studied. Alternatively, a split dosing schedule (e.g., BID) may be studied at the current dose level under study or previously studied daily dose levels. Should more than 3 patients be accrued to a dose level for reasons other than DLT/toxicity, the decision to escalate further may be made after the first 3 patients clear the DLT window period after review of the available data by the Study Committee.

Once the safety and tolerability of a dose level of PLX9486 in combination with PLX3397 have been established by 3 to 6 patients treated for 28 days (one cycle), intra-patient dose escalation to the next dose level may be permitted for patients at lower dose levels who have not experienced a Grade 3 or higher treatment-related toxicity that has not resolved.

Part 2e. Cohorts of patients will be enrolled using the standard “3+3” design. The PLX9486 dose escalation may follow the pattern established in Part 1, starting at 50% of the MTD/RP2D established in Part 1. In the absence of Grade ≥ 2 toxicity that is considered “possibly” or “probably” related to the study agent and in conjunction with review of the pharmacokinetic data, dose escalation in Part 2e is planned to occur as indicated in [Table 18](#).

Table 18: PLX9486 and Sunitinib Administration in Part 2e: Initial and Potential Dose-escalation Cohorts

Cohort Number	PLX9486 Dose Level (mg/day) ^a	Sunitinib Dose Level (mg/day)
1	Approximately 50% of Part 1 RP2D	25
2	100% of Part 1 RP2D	25
3	100% of Part 1 RP2D	37.5

RP2D = recommended phase 2 dose

^a Dosing interval/frequency will be QD unless otherwise specified (e.g., BID dosing).

[figure not shown]
Dose escalation will continue unless there are dose-limiting toxicities in ≥ 2 of 6 patients in one cohort within the first 28 days of continuous dosing.

Further dose escalation and reduction in smaller increments may be undertaken at any time based upon emerging safety, PK, and PD data. Dose adjustments may also include increasing the number of subjects at a given dose level as a result of the review of safety and PK data by the Sponsor and investigators. In addition, alternative dosing schedules may be explored, such as continuous dosing followed by a rest period, staggered dosing of the agents, etc., depending on the safety, PK, or PD-generated data.

If a DLT is observed in one patient at a given cohort, an additional 3 patients will be enrolled into the cohort. If DLT is observed in ≥ 2 of at least 6 patients (i.e., $\geq 33\%$) at a dose level, then a lower dose level of PLX9486 may be introduced to the combination regimen. If no DLT is observed, the recommended dose for further evaluation may be established based on toxicity, PK, and convenience of dosing in approximately 3 to 6 patients treated at that dose. Dose escalation will only be permitted if adequate safety and tolerability have been demonstrated at the previous lower dose for 28 days.

In addition, if the Study Committee ([Section 10.1.1](#)) determines that, in the absence of DLTs, enrollment of additional patients is required in order to better understand PK, safety, or pharmacodynamic markers in specific patient types (e.g., patients with exon 17 mutations), an additional 3 patients may be undertaken at one or more of the dose levels already studied or currently being studied. Alternatively, a split dosing schedule (e.g., BID) may be studied at the current dose level under study or previously studied daily dose levels. Should more than 3 patients be accrued to a dose level for reasons other than DLT/toxicity, the decision to escalate further may be made after the first 3 patients clear the DLT window period after review of the available data by the Study Committee.

Once the safety and tolerability of a dose level of PLX9486 in combination with sunitinib have been established by 3 to 6 patients treated for 28 days (one cycle), intra-patient dose escalation to the next dose level may be permitted for patients at lower dose levels who have not experienced a Grade 3 or higher treatment-related toxicity that has not resolved.

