9.2.2 Dose Escalation Rules

Dose escalation will occur in accordance with the rules listed below.

- The DLT window is 28 days.
- A minimum of 3 patients will be initially enrolled per cohort.

- If 1 of the first 3 patients enrolled in a given cohort experiences a DLT, at least 3 additional patients will be enrolled in that cohort.
- If less than one-third of evaluable patients in a given cohort experiences a DLT (e.g., DLTs in 0 of 3 or \leq 1 of 6 patients), escalation will proceed to the next higher dose level.
- If a DLT is observed in one-third (e.g., 33%) or more of patients (e.g., 2 or more of up to 6 patients), the dose combination at which this occurs will be considered intolerable and the MTD will have been exceeded.
- The highest dose level at which 0 or 1 of 6 experience a DLT will be declared the MTD. If only 3 patients were initially evaluated at that dose level, an additional 3 patients will be enrolled to evaluate for DLTs at that dose level.
- After dosing has been completed in each cohort, safety and PK data (as applicable) will be reviewed by and dose escalations decisions made by the Sponsor, and investigators and study staff from all participating sites.
- If \geq 2 patients in one cohort experience \geq Grade 2 toxicities that are considered possibly or probably related to PLX9486, PLX9486 combined with PLX3397, or PLX9486 and sunitinib within the first 28 days, the study committee will determine the dose escalation increment after review of the safety, PK, and PD data.

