10.3 Treatment Group Assignments

This is an open-label, sequential dose-escalation study with extension cohorts. The initial dose level of PLX9486 will be 250 mg/day. Thereafter, dose-escalation groups will occur as described in [Section 9.2.1](#). Extension cohorts will be enrolled in parallel at the RP2D according to inclusion and exclusion criteria ([Section 8.1](#) and [Section 8.2](#)). The initial dose of PLX3397 will be 600 mg/day administered BID. Thereafter, dose escalation groups will occur as described in [Section 9.2.1.2](#). For the combination cohort with sunitinib the initial sunitinib dose will be 25 mg/day. Further details may be found in [Section 9.2.1.2](#).

10.4 Withdrawal of Patients from Drug Treatment or from the Study and Patient Replacement

The Plexxikon Medical Monitor will monitor safety data throughout the course of the study. The Medical Monitor will review SAEs within timeframes mandated by company procedures and will review trends, laboratory data, and AEs at periodic intervals and provide for interim safety analyses if appropriate.

The reasons a patient may discontinue or be withdrawn from the study include, but are not limited to, adverse event, clinically significant disease progression, patient request, investigator decision, protocol violation, patient noncompliance, and study termination by the Sponsor or institutional review board (IRB)/independent ethics committee (IEC). When a patient discontinues or is withdrawn, the investigator will notify the Sponsor and should perform the procedures indicated in the End of Study column in the Schedule of Events within 30 days after discontinuation of study drug and before initiation of any new anti-cancer therapy. Follow-up information will be obtained for patients who discontinue their participation in or are withdrawn from the study.

Patients withdrawn from the study for reasons other than toxicity or clinically significant disease progression (e.g., protocol violation or noncompliance) may be replaced at the discretion of the medical monitor and the investigator. Study drug administration may be discontinued due to an adverse event or at the discretion of the investigator.

The consequence of withdrawal of consent by a patient will be that no new information will be collected from that patient and added to the existing data or any database. However, every effort will be made to follow all patients for safety.

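### Part 2b Cohort 3 is cleared for DLTs at PLX3397 400 mg QD, but the same row allows 600 mg QD from Cycle 3; the plan does not say which dose a pass supports, and no liver chemistry is scheduled for about 28 days after the step.

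*Protocol*

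**What the plan says.** Table 17 (Section 9.2.1.2) gives Cohort 3 as 100% of the Part 1 RP2D of PLX9486 with PLX3397 "400 mg QD (Cycles 1 and 2"), followed by "600 mg QD (Cycle 3" onward). Footnote b sets the condition for the step: "At the discretion of the investigator and in the absence of clinically significant drug-related toxicity" during the first two cycles.

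Section 9.3 restricts DLTs to Cycle 1, and Section 9.2.2 sets a 28-day window. Section 9.2.2 then states: "The highest dose level at which 0 or 1 of 6 experience a DLT will be declared the MTD". Toxicity after Cycle 1 is not ignored. Section 9.3 has it reviewed, the synopsis stopping rules take it into account, and Section 9.4 makes it an input to the RP2D. None of these sets a count or limit.

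Table 3 has chemistry weekly in Cycles 1 and 2 and on Day 1 only from Cycle 3. From C5D1 it may be every 8 weeks. Section 5.10 ties the closer monitoring to the first 8 weeks on PLX3397.

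On schedule, Section 9.1.2 says "As of Amendment 6, PLX3397 should be administered once a day" and moves patients already on BID to QD. Three other places still describe split dosing:
- Table 17, Cohort 2: "600 (200 mg in AM and 400 mg in PM")
- Section 9.1.4: "the evening dose of PLX3397 will be taken by the subject at home"
- Section 10.3: "The initial dose of PLX3397 will be 600 mg/day administered BID"

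**The concern.** The primary endpoints of Part 2b include the RP2D of the combination. Cohort 3 is one row with two PLX3397 doses, and only the lower one is taken in the DLT window. If the row clears, Section 9.2.2 does not say whether the result belongs to 100%/400 mg QD or to the whole row. The row also comes after Cohort 2 (600 mg/day) while starting lower, so it is unclear which of the two is the higher level.

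The second issue is when blood is drawn. Section 5.6.1 describes cholestatic liver injury with PLX3397, including one transplantation and one death with ongoing injury. The optional increase falls exactly where the chemistry schedule thins out. Table 24 acts from Grade 2 ALT or AST, but only once a sample has been taken.

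**Working it through.** **1. The plan's own operating characteristics.** For a 3+3 cohort that clears on 0/3, or on 1/3 followed by 0/3, with true DLT rate p:

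P(clear) = (1−p)³ + 3p(1−p)² × (1−p)³

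| p | 10% | 20% | 30% | 40% | 50% | 60% | 70% |
|---|---|---|---|---|---|---|---|
| Table 29 | 0.91 | 0.71 | 0.49 | 0.31 | 0.17 | 0.08 | 0.03 |
| Recomputed | 0.906 | 0.709 | 0.494 | 0.309 | 0.172 | 0.082 | 0.032 |

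Table 29 reproduces. For Cohort 3, p is the 28-day DLT rate at 400 mg QD, so the table says nothing about the 600 mg QD stage. To illustrate with assumed rates (the protocol gives none): at 10% for 400 mg QD, Cohort 3 clears with probability 0.91 whatever the rate at 600 mg QD. A separate window at 600 mg QD would clear with probability 0.71, 0.49 or 0.31 if the rate there were 20%, 30% or 40%.

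**2. Size of the step.** 600/400 = 1.5, an increase of 50%.

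**3. Chemistry around the step.** Study day = 28 × (cycle − 1) + day, so C3D1 = 57, C4D1 = 85 and C5D1 = 113.
- In the 8 weeks after starting 400 mg: Days 8, 15, 22, 29, 36, 43 and 50, which is 7 tests.
- In the 8 weeks after starting 600 mg: Day 85 only, which is 1 test.
- Gap from step to first test: 85 − 57 = 28 days, or 21 to 35 if C4D1 moves by its ±7-day window around a fixed C3D1.

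The Table 3 grid is partly scrambled in the text available, and the C1D22 cell is uncertain; without it the first count is 6. Table 26 supports 7: its total in the Day 22 position is 19 mL = 8 + 8 + 3 (hematology, chemistry, PK). The 28-day gap does not depend on this cell.

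**4. Safety data in the protocol.** Section 5.5.1.2 reports 0 DLTs in 11 patients to December 2017. The exact two-sided 95% upper limit is 1 − 0.025^(1/11) = 0.285. Table 12 lists 4 + 8 = 12 enrolled, which would give 1 − 0.025^(1/12) = 0.265. All 11 took PLX9486 500 mg with PLX3397 600 mg/day as a split dose. Their PLX9486 steady-state AUC0-24 of 18,700 to 20,300 ng·hr/mL is 87% to 94% of the 21,500 seen at 1000 mg QD alone (18,700/21,500 = 0.870; 20,300/21,500 = 0.944). The synopsis extends the record to 26 April 2019 and 49 patients across all parts: the only DLT was in Part 1, and the only treatment-related SAE was on the sunitinib combination.

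**The case against.** Five points on the other side deserve weight.

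- A reader might infer that 100%/600 mg QD is reached only in Cohort 3 from Cycle 3, and so never inside a DLT window. The protocol does not support that. Under the Section 9.1.2 switch to QD, a Cohort 2 patient dosed now would take about 100%/600 mg QD from Cycle 1. The BID wording elsewhere is mainly left over from before Amendment 6. What remains is that the protocol reports no result for that pair: the patients described to December 2017 all took PLX9486 500 mg, and the April 2019 summary is not split by dose.
- Section 9.3 evaluates DLTs by cohort and by dosing schedule, and Section 9.4 brings later toxicity into the RP2D. A careful committee would read a Cohort 3 pass correctly. This narrows the labelling point but does not close it, because the MTD sentence in Section 9.2.2 still refers to a row with two doses.
- No part of the protocol reopens a DLT window after intra-patient escalation, and Cohort 3 asks for two clean cycles first. That is fair, and a formal new window is not needed.
- Cholestasis is documented in the first 8 weeks of therapy, which the lead-in covers with the closest monitoring. Nothing says the risk restarts with a dose increase, and the call in Section 5.6.1 for frequent laboratory monitoring sets no interval, so Table 3 does not contradict it. Equally, those 8 weeks are spent at 400 mg and say little about 600 mg QD.
- The April 2019 review was used to support less frequent surveillance. Its SAE record is real reassurance. Its DLT count cannot speak to a Cycle 3 step, since DLTs are Cycle 1 events.

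**Conclusion.** The point holds as a labelling and monitoring gap. A Cohort 3 pass is evidence for 100%/400 mg QD, and the plan should say so. After an optional 50% increase of a hepatotoxic drug, the first scheduled liver test comes about 28 days later, and there is 1 test in 8 weeks against 7 (or 6) after the 400 mg start.

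It would go too far to conclude that the step-up is unsafe or that later toxicity is disregarded. The protocol reports no DLT or treatment-related SAE on the PLX3397 combination to April 2019, and later toxicity is considered for the RP2D. The conclusion rests on the Table 3 schedule having Day 1 chemistry only from Cycle 3, and on no document outside the protocol adding tests after the step. The number of patients who stepped up is not given, so the number affected is unknown.

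**What to change.** 1. In Table 17 and Section 9.2.2, state that a Cohort 3 Cycle 1 pass supports 100%/400 mg QD. When setting the RP2D, summarise toxicity after the step to 600 mg QD separately. Rest any statement about 100%/600 mg on a Cycle 1 assessment at that dose, which Cohort 2 given QD under Section 9.1.2 would provide. If enrolment is over, apply the same labelling in the report.
2. Add a Table 3 footnote requiring liver chemistry in the first cycle after the step-up, for example on Days 8, 15 and 22 (study days 64, 71 and 78), with local draws acceptable. At 8 mL each (Table 26) this is 3 × 8 = 24 mL. Weekly draws for two full cycles would be more than the evidence requires.
3. As a consistency correction, align Table 17 Cohort 2, Section 9.1.4 and Section 10.3 with the QD rule in Section 9.1.2.

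The cost is wording plus a few extra draws or visits for patients who step up. One draw can share the Day 15 PK visit if Table 3 footnote 16 is applied to the step. The 400 mg lead-in stays and no cohort is added.
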